### b. Pilot Data

Pilot data from our laboratory show that enhancing the hippocampal network with rTMS via the PPC (Wang et al., 2014) is effective and replicable: Nine subjects tested showed significant FC increases between the hippocampus and regions that showed a group-level increase in FC with the hippocampus in Wang et al. (precuneus and medial occipital cortex;  $t(8) = 2.73, p < 0.05, d = 0.75$ ; Fig. 4). To show that these effects were specific to the hippocampus, we calculated FC changes between the dorsolateral prefrontal cortex and the same regions (i.e. precuneus and medial occipital cortex), and found no change from pre- to post-stimulation ( $p = 0.22$ ). Furthermore, the increase in hippocampus FC with the precuneus/medial occipital cortex were significantly greater than the change in global connectedness of the brain ( $t(8) = 2.62, p < 0.05, d = 0.58$ ), showing that these effects were network-specific.

These pilot data, however, also suggest rTMS targeted to the hippocampus and connected areas also affects the striatal network. Figure 4 shows statistically significant FC increases between the *caudate* and the precuneus/medial occipital cortex. Thus, in addition to increasing FC in the hippocampal network, rTMS also caused the striatum to be pulled into tighter association with the hippocampal network.

[figure not shown]

Figure 3. Hippocampal FC changes from Wang et al. (2014)  
Stimulation-dependent enhancement of hippocampal network overlaid on a template brain from Wang et al. (2014). The highlighted regions represent the areas that increased in FC with the hippocampus caused by PPC stimulation.

Structural equation modeling, which can be used to determine the direction of influence between network nodes, indicated a robust increase in connectivity from the striatum to the precuneus and medial occipital cortex after stimulation. This may explain why behavioral engagement of the hippocampal network interferes with procedural learning (Brown & Robertson, 2007; Poldrack et al., 2001). Based on these preliminary findings, we will guide rTMS to the hippocampal network and examine the effects on both the hippocampal-dependent memory system and the striatal memory system. We will also target the striatal network, and look for similar effects on the hippocampal network.

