### iv. rTMS

The parietal target in Experiments 1 and 3 will be the region of the left PPC with the greatest connectivity with the left hippocampus derived from the baseline resting-state fMRI session, (similar to Wang et al. 2014). The left PPC was chosen because of its dense connections with the hippocampus (Cavada & Goldman-Racic, 1989; Mesulam et al., 1977).

The target in Experiments 2 and 4 will be the M1 area of maximal connectivity with the right striatum. M1 has extensive projections to the striatum (Parent & Hazrati, 1995), and these regions are functionally connected at rest (Di Martino et al., 2008).

rTMS targets will be marked in the participant's anatomical MRI volume and located with a frameless stereotaxic system. If any experiment, for any reason, fails to produce useful individual targets, a literature-based location for the parietal cortex (Wang, et al., 2014) or motor cortex will be used as our location of stimulation. To reduce the influence of diurnal variations in the responsiveness to neuroplasticity protocols (Sale, Ridding, & Nordstrom, 2008), we will make every effort to test subjects during the same time of day.

*20-Hz Stimulation (facilitation)* will be delivered at 100% of the motor evoked potential threshold and 20-Hz in trains lasting 2 s for 20 min with 28 second rests in-between trains (similar to Wang et al., 2014).

*Continuous Theta-Burst Stimulation (cTBS; inhibition)* will be delivered at 80% of active motor threshold for 40 seconds (similar to Huang et al., 2005). cTBS consists of 50-Hz triplets separated by 200ms.

*Control stimulation.* As a negative control, rTMS will be delivered to the vertex with the same delivery parameter values and neuronavigation. Wang and colleagues (2014) used vertex stimulation as a control condition and found no significant effects on rsFC or behavior. In addition, there is no evidence that vertex stimulation causes other changes in rsFC (Jung et al., 2016).

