## **10. Statistical Analysis**

### **a. Analysis of data/ study outcomes**

Our primary aim is to examine stimulation-dependent changes in FC within the targeted network in each study. Secondary aims for this protocol will include all behavioral change data from the WPT-F and WPT-O and changes in FC to the non-targeted network, and between networks.

To calculate FC from resting-state scans, the Pearson correlation coefficients ( $r$ ) between time courses of BOLD activity in a seed region (i.e. hippocampus or striatum) will be calculated to determine the FC before and after rTMS stimulation. They will be Fisher-transformed to normalize  $r$ -values.

To calculate FC from task-based scans, the time series from a seed region will be inputted into a general linear model analysis as a regressor along with a regressor indicating when the task is occurring. For the WPT-F, this will include both the choice phase and the feedback phase during learning. For the WPT-O, this will include the observational trials and the retrieval trials. This analysis will be performed on each

individual to create a spatial map of beta values indicating the strength of the association between the seed and other regions during task performance.

*Statistical analysis for Experiments 1 and 3 (targeting the hippocampal network)*

iv. Preliminary Aims

Primary Aim 1

To confirm modulation of the hippocampal network, the average timeseries of the left hippocampal seed will be correlated with all other voxels with available data before and after stimulation. These data will be submitted to AFNI's 3dLME linear mixed effects function, which will be used to reveal potential areas of significant change in rsFC and tbFC.

v. Secondary Aims

Secondary Aims

Behavioral data will be submitted to a 3 x 2 x 2 ANOVA using timepoint (Pre-stimulation, post-stimulation, and follow-up), group (PPC vs. Vertex), and learning type (procedural and declarative) as factors. A significant interaction ( $p < 0.05$ ) between time, group, and learning type will confirm network-dependent modulation of each memory type.

To confirm changes in FC, a similar analysis will be performed as Primary Aim 1, except that the timeseries of the right striatum seed will be used instead of the hippocampal seed.

*Statistical Analysis for Experiments 2 and 4 (targeting the striatal network)*

i. Preliminary Aims

Preliminary Aim 1

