### **b. Power analysis (All experiments)**

All experiments in this protocol are powered based on the primary outcome, which relates to modulating FC within the targeted networks.

A power analysis was conducted on our preliminary data using G\*Power v3.1. We used a repeated-measures ANOVA model with FC changes between the hippocampus and the precuneus/medial occipital cortex as my dependent variable. The precuneus/medial occipital cortex was used because these regions showed the most robust response to stimulation in Wang et al., (2014). Based on these data (Mean Difference = 0.16, Pooled Standard Deviation = 0.21, Cohen's  $d = 0.75$ ), and assuming power of 0.80 and  $\alpha = 0.05$ , 26 right-handed healthy participants between 18 and 40 years of age will be needed (13 per group) for each experiment (104 total). To account for attrition (estimated ~15%), we will request an accrual ceiling of 122.

There were no preliminary data to conduct a power analysis for stimulation involving the striatal network. Thus, we propose to have 13 analyzable subjects in the M1 group, the same number as in the parietal group from Experiments 1 and 3. We also plan to obtain 13 subjects in the control group, resulting in 26 analyzable healthy subjects (13 per group).

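### The FC analysis names no baseline adjustment and no active-versus-vertex contrast; adjusting for each participant's own baseline FC would gain precision from data already collected

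*Combined protocol and SAP*

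**What the plan says.** Section 9.a defines the primary outcome as pre-to-post rTMS differences in resting-state and task-based FC within the targeted network.

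For Experiments 1 and 3, section 10.a says that the average hippocampal seed series "will be correlated with all other voxels with available data before and after stimulation", and that the data then go to AFNI's 3dLME to find areas of significant change. Experiments 2 and 4 use the same wording with the striatal seed. No fixed effects, covariates or contrasts are listed for this model. The Précis says that active rTMS will be compared with vertex sham, but section 10.a does not carry that comparison into the FC model.

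For behaviour, section 10.a is explicit: a 3 x 2 x 2 ANOVA with timepoint (including pre-stimulation), group and learning type as factors.

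Section 10.b says: "We used a repeated-measures ANOVA model with FC changes" as the dependent variable. Its inputs are "Mean Difference = 0.16, Pooled Standard Deviation = 0.21" and d = 0.75, "assuming power of 0.80 and" alpha of 0.05, and it concludes that 26 participants "will be needed (13 per group) for each experiment (104 total").

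On controls, section 4.d.iv says "rTMS will be delivered to the vertex with the same delivery parameter values and neuronavigation". Section 10.b gives each experiment its own 13 vertex participants and does not mention sharing them.

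**The concern.** Every cue in the plan points to an analysis of change: the outcome definition, the before-and-after entry into the model, and the power calculation. An unconstrained group by time comparison of two scans amounts to comparing change scores between groups. A change score subtracts baseline with a slope of 1. With equal pre and post SDs, the efficient slope is the pre-post correlation, which is below 1.

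With 13 per arm this matters. The standard error of a chance baseline difference between arms is sqrt(2/13) = 0.39 SD. On the protocol's SD of 0.21 that is 0.08 FC units, half of the 0.16 effect that the trial is planned to detect. Baseline FC is scanned in everyone, so the information needed to handle such imbalance efficiently is already in hand.

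**Working it through.** **Inputs**
- Mean difference 0.16, pooled SD 0.21, d = 0.75, alpha 0.05, power 0.80, 13 per group (section 10.b).
- Pilot pre-to-post test in nine people: "t(8) = 2.73, p < 0.05, d = 0.75" (section 1.b).
- Assumptions: 0.21 is the SD at a single time point and is equal before and after; no change under vertex; two-sided 0.05; one region.

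**The plan's own figure.** A two-sample t test at d = 0.75 needs 29 per group for 80% power; 13 per group gives 0.45. A G*Power-style group by time test with f = d/2 = 0.375 gives N = 18 in total at two measurements and correlation 0.5. It gives N = 26 only with settings that the plan does not state (two measurements and correlation 0.2, or three measurements and correlation 0). So 26 does not follow from the stated inputs, but it can be reached with undeclared ones, and I do not call it an arithmetic error.

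**Implied pre-post correlation**
- Standardised paired change: 2.73/sqrt(9) = 0.91.
- SD of change: 0.16/0.91 = 0.176.
- SD of change squared = 2 x SD² x (1 − r), so r = 1 − 0.176²/(2 x 0.21²) = 0.65.

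**Variance with and without adjustment**
- Change score: 2 x SD² x (1 − r).
- Baseline-adjusted: SD² x (1 − r²).
- Ratio: (1 + r)/2 = 0.825 at r = 0.65, a saving of 17.5%.
- Standardised effects at r = 0.65: 0.91 for change, 0.16/(0.21 x sqrt(1 − 0.65²)) = 1.00 adjusted.

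**Power at 13 v 13 (noncentral t)**

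| r | Variance saved | Change score | Baseline-adjusted |
|---|---|---|---|
| 0.4 | 30% | 0.40 | 0.53 |
| 0.5 | 25% | 0.46 | 0.57 |
| 0.65 | 17.5% | 0.61 | 0.69 |
| 0.8 | 10% | 0.84 | 0.87 |

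If 0.21 is instead the SD of change, unadjusted power is 0.46 and adjusted power is 0.50 (r = 0.8) to 0.64 (r = 0.3).

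**Pooling the vertex arms of Experiments 1 and 2.** The PPC active arm exists only in Experiment 1 and the M1 active arm only in Experiment 2. With a fixed experiment term, the four cells take four parameters, so each active arm is again compared only with its own 13 controls. The variance factor of the contrast is 1/13 + 1/13 = 0.154, as without pooling. Power at r = 0.65 is 0.62 unadjusted and 0.71 adjusted; the slight rise comes only from extra error degrees of freedom. Without the experiment term the factor is 1/13 + 1/26 = 0.115, and power is 0.74 unadjusted and 0.82 adjusted. That gain assumes no cohort or period difference between the experiments. Even then, power with both changes is 0.66 at r = 0.4, 0.71 at r = 0.5 and 0.78 at r = 0.6.

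**The case against.** The strongest reply is that section 10.a does not specify a change-score test. It leaves the 3dLME model open, and a mixed model with a common baseline mean would fit its wording and be about as efficient as ANCOVA. Section 10.b describes a sample-size calculation, not the analysis model. This stands: the plan is silent on baseline adjustment and does not exclude it, so the loss is conditional for FC. For WPT scores the ANOVA is written out, and the point applies directly.

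The correlation of 0.65 is also weak evidence. It comes from nine people and an assumption of equal SDs; a Fisher 95% interval runs from about −0.02 to 0.92. Section 1.a argues that FC is highly reliable across sessions without giving a coefficient, and high reliability would shrink the gain. This stands for the size. Under the equal-SD model the direction does not reverse at any r below 1.

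Baseline adjustment is free only under random allocation. Otherwise ANCOVA and change-score analyses can estimate different quantities. The documents describe no randomisation, so this condition has to be carried with the recommendation.

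A reader might also infer that the vertex arms are interchangeable, and that sharing them together with baseline adjustment would deliver the stated 0.80. The documents do not support that. The arms match only in pairs: 20-Hz in Experiments 1 and 2, and Experiments 3 and 4 only if both end with the same inhibitory type. No concurrent enrolment or common allocation across experiments is described, and a safeguarding experiment term removes the gain in contrast variance.

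**Conclusion.** The point holds as a conditional precision loss with a better method available. The plan frames the primary outcome as a difference from baseline and does not say how baseline enters the FC model or which contrast is tested. If the model is an unconstrained group by time comparison, baseline adjustment would cut its variance by about 17.5% at r = 0.65 (30% at r = 0.4, 10% at r = 0.8) with the same participants. On the assumptions listed, adjusted power at r = 0.65 is 0.69, so adjustment alone does not bring the active-versus-vertex test to 0.80 there. All the powers are for one region at unadjusted 0.05; the planned voxelwise search over resting-state and task-based FC would have less. Pooling vertex arms can be at most a supportive analysis.

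**What to change.** In section 10.a, write out the FC model and name the primary contrast: active versus vertex at the post-stimulation scan, adjusted for the participant's own baseline FC. Either of two forms will do:
- ANCOVA on the network-average FC, with baseline FC as covariate.
- A mixed model with a common pre-stimulation mean across groups. This form also accommodates participants with only a first session, whose data section 8 says will be kept and analysed.

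Analyse WPT scores the same way. Where baseline is repeated after rescheduling (section 4.b.i), say which measurement is used. State whether allocation to active or vertex is random, since the adjustment relies on it. In section 10.b, restate the power calculation with the assumed pre-post correlation and a range.

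Keep the primary analysis of each experiment to its own vertex arm. If a pooled vertex comparison is wanted, label it supportive and fit it without an experiment term. Use it for Experiments 1 and 2 only if they enrol concurrently under common random allocation; for Experiments 3 and 4, both must also use the same inhibitory type.

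The cost of the main change is SAP wording: no extra participants, scans or visits.

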#### Précis:

#### Objective

The Behavioral Neurology Unit studies the human brain systems underlying learning and adaptation with the ultimate goal of finding interventions to make these processes more efficient. We are interested in whether repetitive transcranial magnetic stimulation (rTMS) can alter functional connectivity (FC) and behavioral efficiency in two memory networks in the brain: the hippocampal network, which supports the storage and retrieval of recallable facts, concepts, and events, and the striatal network, which supports the storage and retrieval of skills and habits. Additionally, because these networks interact behaviorally and can interfere with each other, an important question is whether neuromodulation of one network changes connectivity and efficiency in the other network. Pilot data from our group suggest that exogenous stimulation of one network causes it to expand its range of FC and co-opt resources from the other, which is a potential mechanism for the observed behavioral interaction. This study is designed to test a) whether rTMS- modulates within-network FC and memory supported by that network, and b) whether this also causes FC and behavioral changes in the other network.

**Study population:** Healthy Volunteers

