#### Design

This study contains four between-subjects experiments and is a mixed inter-/intra subject design. Experiment 1 will use nominally excitatory stimulation targeting the hippocampal network to increase FC within the hippocampal network. We also expect to increase FC between the hippocampal and striatal networks, increased declarative memory, and a possible decrease in procedural, learning. Experiment 2 will use excitatory stimulation targeted to the striatal network. We expect this to cause stronger within-network FC in the striatal network, increased FC between the hippocampus and the striatal network and concomitant behavioral effects. Experiments 3 and 4 will be similar except that we will target nominally inhibitory stimulation to these networks and look for the inverse results. FC will be measured under resting and task-activated conditions and active rTMS will be compared to vertex sham.

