field, rTMS affects network-level activity beyond the site of stimulation (Fox et al., 2012). By applying rTMS to a cortical site known to be connected to a network of interest, it is possible to modulate the FC of that network (Eldaeif et al., 2011; Rahnev et al., 2013; Steel et al., 2016; van der Werf et al., 2010; Vercammen et al., 2010). Wang, and colleagues (2014) delivered nominally excitatory (20 Hz) rTMS to the subject-specific posterior parietal cortex (PPC) site that was maximally connected to the anterior hippocampus and observed robust increases in hippocampal network FC. Specifically, this technique increased resting-state FC (rsFC) between the hippocampus and several cortical regions (Fig. 3 Image showing Stimulation-dependent enhancement of hippocampal network). These changes were specific to the hippocampal network, and not the local site of stimulation, as the voxels throughout the brain with the highest baseline FC with the hippocampus showed the largest FC increase. Furthermore, these effects were present two-weeks later (Wang & Voss, 2015). The validity of using rsFC of a cortical area with a deep node (the hippocampus) as a subject-specific targeting guide and then using the change in FC as an outcome measure has been established by Wang et al (2014) and confirmed in our laboratory (see pilot data below).

Using this technique, we will attempt to increase and decrease FC within the hippocampal and striatal memory systems by selectively targeting each network with rTMS in separate experiments. We predict that rTMS will cause changes in FC and memory in the targeted network, which correspond with the stimulation protocol: Nominally excitatory stimulation will cause enhancement of the targeted network, and nominally inhibitory stimulation will cause FC to decrease. Additionally, because these networks are known to interact in behavioral and imaging experiments (Brown & Robertson, 2007; Cohen & Robertson, 2011; Mattfeld & Stark, 2010, 2015; Poldrack et al., 2001), we expect that altering the function of one network will cause changes in the pattern of FC in the other. Pilot data from our laboratory (Fig. 4 Connectivity changes with left Precuneus and medial Occipital Cortex) show that declarative

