**b. Secondary aims**

Our secondary aims are to measure the effects of each type of stimulation at each site on declarative and procedural learning and memory and between network changes in task-based and resting-state FC.

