### **b. Secondary outcome measures**

- Pre-to-Post rTMS differences in WPT-O scores
- Pre-to-Post rTMS differences in WPT-F scores
- Pre-to-Post rTMS differences in rsFC and tbFC between memory networks.

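### The three-way interaction shows only that the two memory tasks respond differently, not that each was modulated, and no test of either task alone is planned

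*Combined protocol and SAP*

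**What the plan says.** For Experiments 1 and 3, and again for Experiments 2 and 4, section 10.a plans one ANOVA of the behavioural data with timepoint (three levels), group (active site or vertex) and learning type (procedural or declarative) as factors. The only decision rule is that an interaction significant at p < 0.05 "between time, group, and learning type will confirm network-dependent modulation of each memory type".

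Other sections treat the two tasks as separate questions:

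- Section 9.b lists "Pre-to-Post rTMS differences in WPT-O scores" and "Pre-to-Post rTMS differences in WPT-F scores" as two secondary outcomes.
- Section 2.b aims to "measure the effects of each type of stimulation at each site on declarative and procedural learning and memory".
- The Précis (Objective) asks, as the second of two study questions, "whether this also causes FC and behavioral changes in the other network".
- The Précis (Design) expects, for Experiment 1, "increased declarative memory, and a possible decrease in procedural, learning".

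No test of either task alone is described in section 10 or elsewhere. The only other planned uses of the task scores are exploratory: as predictors of FC change (section 2.c) and as correlates of it (section 9.c).

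**The concern.** The interaction answers one question: is the effect of stimulation over time different for the two tasks? The plan reads a positive answer as showing that both memory types were modulated. That does not follow. A difference can arise because one task moved and the other stayed still. It can also arise from a change opposite to the prediction, because the F test has no direction. Conversely, if stimulation moves both tasks by the same amount there is no difference to detect, although both memory types were modulated. The interaction is therefore neither sufficient nor necessary for the stated conclusion.

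Followed literally, the plan could report modulation of both memory types when only one changed, and could leave modulation unconfirmed when both changed alike. Whether behaviour changes in the non-targeted network needs a result for that task by itself, and the plan produces none.

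**Working it through.** **1. What is tested.** Let D be the active-minus-vertex change on WPT-O and P the same on WPT-F. The three-way interaction tests D − P = 0 over the time contrasts. It tests neither D = 0 nor P = 0.

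**2. Inputs.** From the documents: 13 per group (section 10.b), alpha 0.05 and three timepoints (section 10.a). The plan states no behavioural effect, SD or power, so there is no planned figure to reproduce. Assumed:

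- each task has SD 1 at each visit, with the tasks on a common scale;
- the correlation ρ between any two visits is 0.3 to 0.8;
- the correlation r between tasks is 0 to 0.3;
- the cross-task covariance is either (A) r times the visit correlation or (B) constant at r across visits.

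**3. Power of the interaction.** Take WPT-O minus WPT-F at each visit. The three-way interaction is the group-by-time F test on this difference, with 2 and 2 × 24 = 48 df. Its error variance is 2(1 − r)(1 − ρ) under A and 2(1 − ρ) under B. If the two task effects differ by δ at post-stimulation only, the group-difference profile (0, δ, 0), centred over time, has sum of squares 2δ²/3. Half of the difference falls in each of two groups, giving 2 × ¼ × 2δ²/3 = δ²/3. Hence

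λ = 13 × (δ²/3) / error variance.

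A change that persists to follow-up, profile (0, δ, δ), gives the same sum of squares and the same result.

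- δ = 1, ρ = 0.3, r = 0: λ = 4.333/1.4 = 3.10, power 0.313.
- δ = 1, ρ = 0.8, r = 0.3 (A): λ = 4.333/0.28 = 15.48, power 0.937.

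One task changes by 1 SD and the other does not:

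| Structure | ρ = 0.3 | 0.5 | 0.65 | 0.8 |
|---|---|---|---|---|
| A, r = 0 (also B, any r) | 0.313 | 0.422 | 0.570 | 0.822 |
| A, r = 0.3 | 0.429 | 0.570 | 0.735 | 0.937 |

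At 0.5 SD the range is 0.109 to 0.382 under A and 0.109 to 0.278 under B. A one-task change of −1 SD gives 0.315 to 0.937 by simulation, the same as +1 SD, so the rule does not see direction.

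**4. Separate tests per task.** Each is a two-sample t test (24 df) on post-minus-pre change. The SD of change is √(2(1 − ρ)), so 1 SD of raw score is 0.85/1.00/1.20/1.58 SD of change at ρ = 0.3/0.5/0.65/0.8. Power for one task is then 54/69/83/97%. Joint results come from simulation, 40,000 trials per cell, over both structures.

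| True state | Planned rule declares both modulated | Both per-task tests significant, unadjusted | Same, with Holm |
|---|---|---|---|
| One task 0.5 SD | 11% to 38% | 0.9% to 2.5% | 0.7% to 2.2% |
| One task 1 SD | 31% to 94% | 2.6% to 5.0% | 2.3% to 4.9% |
| Both tasks +1 SD | about 5% | 29.5% to 94.8% | 28.0% to 94.6% |
| Opposite changes of 0.5 SD | 31% to 94% | 1.8% to 24.1% | 1.4% to 22.7% |

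In the first two rows a claim about both types is false; in the last two it is true. With both tasks at +0.5 SD, unadjusted per-task tests show both in 3.2% to 28.6%. The last row of the planned-rule column uses δ = 0.5 − (−0.5) = 1, so it equals the 1 SD row. Under B alone the upper limits in the first, second and fourth rows of that column are 28%, 82% and 82%.

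**The case against.** The wording can be read as a claim of dissociation, meaning that the stimulation effect depends on memory type. Section 1.a describes competition between the two systems, and the Précis expects opposite movements in Experiment 1. For that hypothesis the interaction is the right test and a much more powerful one: with opposite changes of 0.5 SD it is significant in 31% to 94% of trials, while both separate tests are significant in 2% to 24%. This stands, and it is why the interaction should be kept. It does not rescue the conclusion drawn about each memory type. The Précis calls the procedural decrease only possible, so a one-task effect is a result that the protocol itself anticipates.

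Equal change in both tasks would also not be invisible, because the same ANOVA contains a time-by-group term. On the assumptions above, the mean of the two tasks has error variance (1 + r)(1 − ρ)/2 under A, and (1 − ρ)/2 under B. Power for that term is 77% to over 99% at 1 SD and 25% to 82% at 0.5 SD. But the plan attaches no conclusion to that term, and because it averages over tasks it cannot say which one changed.

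Finally, 1 SD is a large effect: 0.85 to 1.58 SD of change, against d = 0.75 for FC in section 10.b. The 0.5 SD rows (0.42 to 0.79 SD of change) are closer to that figure, so 11% to 38% is the more cautious summary. These are also secondary outcomes, and the study is powered on FC only. Both points limit the severity but do not remove the error.

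**Conclusion.** The concern holds. The decision rule in section 10.a is wrong as written for all four experiments, and the two secondary task outcomes have no analysis of their own. This follows from the contrast being tested and needs no assumed effect size.

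The size does rest on assumptions: 13 per group, equal SDs, compound symmetry over visits, and the stated correlations. On these, a one-task effect leads the rule to declare both memory types modulated in 11% to 38% of trials at 0.5 SD (11% to 28% with constant cross-task covariance) and 31% to 94% at 1 SD (31% to 82%). An equal effect on both tasks leaves the rule at about 5%. Because the outcomes are secondary and the remedy is textual, this should be fixed but does not threaten the primary analysis.

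**What to change.** In both secondary-aims paragraphs of section 10.a:

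- Pre-specify two active-versus-vertex contrasts of change from pre-stimulation to post-stimulation, one for WPT-O and one for WPT-F, each two-sided. Report the 2-week change as a separate contrast.
- Claim modulation of a memory type only from its own contrast. Read it against the predicted direction where one is stated: the Précis (Design), and section 1.a for the targeted network ("We predict that rTMS will cause changes in FC and memory in the targeted network, which correspond with the stimulation protocol"). A significant result in the other direction is reported as contrary to prediction.
- Keep the three-way interaction within the planned ANOVA, described only as the test that the two effects differ.
- State in advance whether Holm is applied across the two contrasts within an experiment. It is optional; its purpose is to control error when neither task changes.

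Only SAP wording changes; the ANOVA, sample size and data collection stay as they are. There are two costs.

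- **Error rate against power.** With two unadjusted tests, the chance of at least one false claim when neither task changes is 9% to 10%. Holm returns it to 5%, but lowers power for a one-task change of 1 SD from 54/69/83/97% to 42/57/74/94% at visit correlations 0.3/0.5/0.65/0.8.
- **Low power for both effects.** With opposite changes of 0.5 SD, both are shown in only 2% to 24% of trials unadjusted and 1% to 23% with Holm. The SAP should say that failure to show both is not evidence of no effect.
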